### 7.2 PARTICIPANT DISCONTINUATION/WITHDRAWAL FROM THE STUDY

Participants are free to discontinue the study at any time, for any reason, and without prejudice to further treatment. The investigator may remove a participant if, in the investigator's judgment, continued participation would pose unacceptable risk to the participant or to the integrity of the study data. Reasons for removal or withdrawal might include:

- Withdrawal of consent
- Administrative decision by the investigator or Sponsor
- Significant protocol deviation
- Participant noncompliance, or other significant protocol deviation
- Safety concern by the investigator or Sponsor
- Lost to follow-up

With the exception of withdrawal of consent, participant withdrawal should be discussed with the Medical Monitor, when possible, prior to withdrawing. Notification of early participant discontinuation from the study and the reason for discontinuation will be made to Allgenesis and will be clearly documented on the appropriate eCRF. If a participant discontinues prior to completing the study, the procedures outlined for the Exit visit should be performed at the last visit the participant attends.

### 7.3 LOST TO FOLLOW-UP

At any point during the trial, if a participant fails to return for a scheduled visit and is unable to be contacted by the site staff, he or she will be considered lost to follow-up. This does not include a single missed visit of which the site was notified or a missed visit with subsequent contact from the participants indicating an intention to continue on the study. The following actions must be taken if a participant fails to return to the clinic for a required study visit:

- The site will attempt to contact the participant and reschedule the missed visit within the visit window and counsel the participant on the importance of maintaining the assigned visit schedule and ascertain if the participant wishes to and/or should continue in the study. If this make-up visit is outside the allowable window, a protocol deviation will be recorded
- Before a participant is deemed lost to follow-up, the investigator or designee will make every effort to regain contact with the participant (where possible, 3 telephone calls and, if necessary, a certified letter to the participant's last known mailing address or local equivalent methods). These contact attempts should be documented in the participant's medical record or study file

- Should the participant continue to be unreachable, he or she will be considered to have withdrawn from the study with a primary reason of lost to follow-up, and a protocol deviation will be recorded

## 8 STUDY ASSESSMENTS AND PROCEDURES

### 8.1 EFFICACY ASSESSMENTS

Refer to the MOP for details on the efficacy measures.

#### 8.1.1 PRIMARY EFFICACY MEASURE

- **Overall conjunctival hyperemia.** Digital slit-lamp photos will be captured and submitted to the central reading center for assessment. Conjunctival hyperemia will be measured in 4 quadrants of the ocular surface and graded using a 5-point scale of 0 = none, 1 = mild, 2 = moderate, 3 = severe, and 4 = very severe. The overall conjunctival hyperemia is the average of the score of each quadrant

#### 8.1.2 SECONDARY EFFICACY MEASURE

- **Localized pterygium conjunctival hyperemia.** Using the above digital slit-lamp photos and grading, the localized pterygium conjunctival hyperemia is the score of the quadrant with the pterygium as assessed by the central reading center.

#### 8.1.3 EXPLORATORY MEASURES

- **Pterygium vascularity.** Using the above digital slit-lamp photos, the vascularity of the body of the pterygium will be quantified by pixel analysis as assessed by the central reading center.
- **Pterygium volume.** AS-OCT images will be captured at selected sites and submitted to the central reading center for assessment of pterygium volume
- **Pterygium vessel length.** Using the above digital slit-lamp photos, the length of the vessels within the pterygium will be assessed by the central reading center

### 8.2 SAFETY AND OTHER ASSESSMENTS

Findings that are of clinical significance will be recorded as AEs on the eCRF. Refer to the MOP for details on the assessments.

- **Demographics.** Includes age, gender, race, ethnicity and lifestyle questions (sun exposure; alcohol, drug and contraceptive use)
- **Physical characteristics.** Includes height and weight measured at screening; weight only at other timepoints indicated
- **Pregnancy testing.** Will be performed using a human chorionic gonadotropin pregnancy urine dipstick test
- **Vital signs.** Includes pulse rate, blood pressure, respiratory rate and temperature
- **Hematology.** Includes hematocrit, hemoglobin, mean corpuscular hemoglobin, mean corpuscular hemoglobin concentration, mean corpuscular volume, platelets, red blood cell (RBC) count, RBC morphology, total white blood cell (WBC) count, and differential (neutrophils, bands, lymphocytes, monocytes, basophils, and eosinophils)
- **Non-fasting serum chemistry.** Includes albumin, alkaline phosphatase, ALT, AST, bicarbonate, calcium, chloride, creatine kinase, creatinine, direct bilirubin, gamma-

glutamyltransferase, indirect bilirubin, magnesium, non-fasting glucose, HgbA1C, phosphorous, potassium, sodium, total bilirubin, total cholesterol, total protein, urea nitrogen, and uric acid

- **Urinalysis.** Includes clarity, color, bilirubin, creatinine, blood, glucose, ketones, leukocyte esterase, nitrite, pH, protein, specific gravity, urobilinogen, microscopic sediment (WBCs, RBCs, casts, bacteria, crystals, and epithelial cells), and screen for drug use
- **Electrocardiogram.** Electrocardiograms will be obtained using a 12-lead standard equipment. The investigator will be responsible for the initial review of the ECG to assess whether the ECG is within the reference limits. All ECGs will be sent to a central reader for interpretation, including confirmation of eligibility and ongoing safety assessments, and assessed for the following measures: P wave, QRS complex, U wave, QRS duration, QT interval, T wave, ST segment, RR interval, PR interval, and qualitative results
- **Participant questionnaire.** The participant will complete a questionnaire querying about the severity of symptoms either in the last month (V1D1) or since the last visit (subsequent visits), including burning/stinging, grittiness, and conjunctival hyperemia, which are scored on a 4-point scale of 0 = none, 1 = mild, 2 = moderate, and 3 = severe. This will be administered prior to application of study drug (visit V1D1 and V3D28, and at any time at other visits) to ensure immediate effects of the eye drops do not confound the results. Any immediate effects of the eye drops will be collected through AE reporting.
- **Best-corrected visual acuity.** Will be quantified using the Early Treatment Diabetic Retinopathy Study visual acuity protocol and the number of letters read correctly will be recorded on the eCRF
- **Intraocular pressure.** Will be measured with a Goldmann applanation tonometer
- **Biomicroscopy.** Will be performed by slit-lamp examination of conjunctiva, cornea, and iris with findings reported on a scale of 0 = none, 0.5 = trace, 1 = mild, 2 = moderate, and 3 = severe. The status of the lens will be assessed using the Age-Related Eye Disease Study scale
- **Tear film break-up time.** Will be performed by instilling between 1.0 to 5.0  $\mu$ L of non-preserved, 2% sodium fluorescein onto the bulbar conjunctiva without inducing reflex. If both eyes are being assessed, the study eye will be assessed first
- **Lissamine green conjunctival staining.** Will be performed using 1 drop (10  $\mu$ L) of 1% lissamine green solution by pipette, with finding reported on a scale of 0 = none, 1 = mild, 2 = moderate, and 3 = severe. If both eyes are being assessed, the study eye will be assessed first
- **Ophthalmoscopy.** A dilated fundus examination will be performed to evaluate any posterior segment abnormalities
- **Plasma drug monitoring.** In a subset of at least 6 participants per study group (at select study sites), blood samples (~10 mL per sample) will be collected for monitoring the plasma concentrations of AG-86893 on Day 1 and Day 28 at pre-dose and at 0.5 and 1 hour after the morning dose from participating participants. At Day 56, a single blood sample will be collected at the study visit. Plasma drug concentrations will be measured using a validated liquid chromatography, tandem mass spectrometry assay, with a target lower limit of quantitation of 0.020 ng/mL. Allgenesis shall have full ownership rights to any biological samples derived from the study.

Unscheduled visits can be included if safety concerns arise. Additional examinations may be performed as necessary to ensure the safety and wellbeing of participants during the study. Electronic Case Report Forms should be completed for each unscheduled visit.

## 8.3 ADVERSE EVENTS AND SERIOUS ADVERSE EVENTS

### 8.3.1 DEFINITION OF ADVERSE EVENTS

An AE is any untoward medical occurrence in a participant or clinical investigation participant administered a pharmaceutical product and that does not necessarily have a causal relationship with this treatment. An AE can therefore be any unfavourable and unintended sign (including an abnormal laboratory finding), symptom, or disease temporally associated with the use of a medicinal (investigational) product, whether or not related to that product. Worsening of the pterygium is not an AE, unless the lesion growth is greater than expected.

### 8.3.2 DEFINITION OF SERIOUS ADVERSE EVENTS

An SAE is any AE occurring at any dose that results in any of the following outcomes: death, a life-threatening AE, inpatient hospitalization or prolongation of existing hospitalization, a persistent or significant disability/incapacity, or a congenital anomaly/birth defect. Important medical events that may not result in death, be life-threatening, or require hospitalization may be considered an SAE when, based upon appropriate medical judgment, they may jeopardize the participant and may require medical or surgical intervention to prevent one of the outcomes listed in this definition. See [Section 8.3.9](#) for procedures for reporting an SAE.

### 8.3.3 CLASSIFICATION OF AN ADVERSE EVENT

#### 8.3.4 SEVERITY OF EVENT

For AEs not included in the protocol-defined grading system, the following guidelines will be used to describe severity.

- **Mild:** Event requires minimal or no treatment and do not interfere with the participant's daily activities
- **Moderate:** Event results in a low level of inconvenience or concern with the therapeutic measures. Moderate events may cause some interference with functioning
- **Severe:** Event interrupts a participant's usual daily activity and may require systemic drug therapy or other treatment. Severe events are usually potentially life-threatening or incapacitating. Of note, the term "severe" does not necessarily equate to "serious"

#### 8.3.5 RELATIONSHIP TO STUDY INTERVENTION

A determination will be made of the relationship (if any) between an AE and the study drug. A causal relationship is present if a determination is made that there is a reasonable possibility that the AE may have been caused by the drug.

- **Not related:** A causal relationship can be excluded and another documented cause of the AE is most plausible
- **Unlikely related:** A causal relationship is improbable and another documented cause of the AE is most plausible
- **Possibly related:** A causal relationship is clinically/biologically plausible and there is a plausible time sequence between onset of the AE and administration of the study drug
- **Related:** A causal relationship is clinically/biologically highly plausible, there is a plausible time sequence between onset of the AE and administration of the study drug, and there is a reasonable response on withdrawal

---

### 8.3.6 EXPECTEDNESS

The investigator will be responsible for determining whether an AE is expected or unexpected based on the information provided in the [Investigator's Brochure](#). An AE will be considered unexpected if the nature, severity, or frequency of the event is not consistent with the risk information previously described for the study intervention.

---

### 8.3.7 TIME PERIOD AND FREQUENCY FOR EVENT ASSESSMENT AND FOLLOW-UP

Any medical condition that is present at the time that the participant is screened will be considered as medical history and not reported as an AE. However, if the study participant's condition deteriorates at any time after the time of Informed Consent, it will be recorded as an AE.

Changes in the severity of an AE will be documented in the source and eCRF to allow an assessment of the duration of the event at each level of severity to be performed. The AE will be recorded in the CRF under the highest level of severity achieved; i.e. if an event progresses from mild to moderate, the severity of the AE will be changed in the CRF, but the date of onset will remain unchanged. Adverse events characterized as intermittent require documentation of onset and duration of each episode.

The collection of AEs and SAEs will commence from the time the Informed Consent Form is signed and continue until the last day of study participation (D84). Events will be followed for outcome information until resolution or stabilization during the study or continue until 7 days (for non-serious AEs) or 30 days (for SAEs) after the last day of study participation (D84).

Adverse events will be monitored throughout the study beginning at the time of Informed Consent. After the first administration of AG-86893, participants will be observed for AEs by remaining in the clinic until at least 1 hour after dosing. At this 1 hour post-initial dose timepoint, and at each post-screening visit, the investigator will begin by querying for AEs by asking each participant a general, non-directed question, such as "How have you been feeling since the last visit?" Directed questioning and examination will then be done as appropriate. All reported AEs will be documented on the appropriate eCRF, including seriousness, severity, relationship to study drug, action taken, and outcome (including date of resolution or stabilization, if AE is not ongoing). If AEs occur, the first concern will be the safety of the study participants.

---

### 8.3.8 ADVERSE EVENT REPORTING

Any AE should be recorded on the appropriate eCRF. All AEs that are drug-related and unexpected (not listed as treatment-related in the current Investigator's Brochure [28]) are to be reported to the governing HREC/IRB/IEC as required by the HREC/IRB/IEC, local regulations, and the governing health authorities.

---

### 8.3.9 SERIOUS ADVERSE EVENT REPORTING

Any SAE occurring during the study period should be immediately (i.e., within 24 hours of learning of the event) reported via the Trial Runners SAE email address listed on the protocol page iii. The SAE is recorded on the appropriate eCRFs. In the event of an early termination within the first 4 weeks after study drug administration, the occurrence of an SAE within 8 weeks from Baseline/Day 1 should be reported immediately to Trial Runners personnel. All participants with an SAE that is related to study drug must be followed for at least 30 days and the outcomes reported until the event is resolved or stabilized. The investigator should supply the sponsor and the HREC/IRB/IEC with any additional requested information (e.g., autopsy reports and terminal medical reports).

In the event of an SAE, the investigator must:

- Notify the Trial Runners safety office and the medical monitor immediately by email using the SAE reporting forms provided by Trial Runners (see page iv of the protocol for the SAE email address). A fax number will be provided for reporting in the event internet access is unavailable during the required reporting period. Emergency phone numbers and relevant personnel contacts are also on page iii of the protocol
- Obtain and maintain in the participant's files all pertinent medical records, information, and medical judgments from colleagues who assisted in the treatment and follow-up of the participant
- Provide Allgenensis with a complete, written case history (SAE report form) which includes a statement as to whether the event was or was not related to the use of the investigational drug
- Promptly inform the governing HREC/IRB/IEC of the SAE if it is drug-related. For other SAEs, notify the governing HREC/IRB/IEC as required by the HREC/IRB/IEC, local regulations, and the governing health authorities

Adverse drug reactions that are both serious and unexpected (suspected unexpected serious adverse reactions [SUSARs]) will be subject to expedited reporting by the Sponsor to HREC and TGA as required by the relevant regulations. TGA reporting must occur within 15 calendar days of first knowledge, or for fatal or life-threatening events, an initial or full report must be made within 7 calendar days and a follow-up report must be made, if necessary, within the 15-calendar day timeframe.

---

#### 8.3.10 REPORTING EVENTS TO PARTICIPANTS

Not applicable.

---

#### 8.3.11 EVENTS OF SPECIAL INTEREST

Based on the observed reversible liver enzyme increases in animal models and humans in a clinical setting using the oral formulation nintedanib, abnormal liver function test results meeting the criteria below will be monitored and may trigger a meeting of the Independent Data Monitoring Committee (IDMC):

- ALT or AST >8x ULN
- ALT or AST >5x ULN for more than 2 weeks
- ALT or AST >3x ULN and (total bilirubin >2x ULN or International Normalized Ratio [INR] >1.5)
- ALT or AST >3x ULN with the appearance of worsening of fatigue, nausea, vomiting, right upper quadrant pain or tenderness, fever, rash, or eosinophilia
- Any other safety signals observed during routine data review that warrant convening of the IDMC, in the opinion of the Medical Monitor

Any of these parameters also represent a trigger for interruption of dose for the participant until the IDMC has been convened and a recommendation provided.

In the event of an increase in serum AST or ALT to >3x ULN, the following monitoring will be required:

- Repeat testing within 48 to 72 hours of ALT, AST, ALP, and total bilirubin to confirm the abnormalities and to determine if they are increasing or decreasing
- Participants will be questioned on the presence of symptoms (eg appearance of worsening of fatigue, nausea, vomiting, right upper quadrant pain or tenderness, fever, rash, or eosinophilia)

- If symptoms persist or repeat testing shows ALT/AST >3x ULN for the participants with normal baseline measures or 2-fold increases above baseline values for participants with elevated values before drug exposure, the following measures will be initiated to determine whether the abnormalities are improving or worsening:
  - Interrupt study treatment dosing until advice from the Medical Monitor is provided
  - Repeat liver tests (ALT, AST, ALP, and total bilirubin) 2 or 3 times weekly. Frequency of testing can decrease to once a week or less if abnormalities stabilize or study drug has been discontinued and participant is asymptomatic
  - Obtain a more detailed history of symptoms and prior or concurrent diseases
  - Obtain a history of concomitant drug use (including nonprescription medications, herbal and dietary supplement preparations), alcohol use, recreational drug use, and special diets
  - Obtain a history of exposure to environmental chemical agents
  - Obtain additional tests to evaluate liver function, as appropriate (e.g., INR)
  - Consider gastroenterology or hepatology consultation

Ocular AEs of special interest include the following and will also be monitored by the Medical Monitor and the IDMC:

- Ocular inflammation, including iritis and uveitis
- $\geq 2$  grade increase in corneal edema, corneal staining or edema
- $\geq 2$  grade increase in any cataract
- IOP change of  $\pm 7$  mmHg from baseline
- Loss of 15 letters or more BCVA

### 8.3.12 REPORTING OF PREGNANCY

If a female participant, or the female partner of a male participant, becomes pregnant during the study, the investigator will notify Trial Runners and the medical monitor immediately after the pregnancy is confirmed and the female participant will be exited from the study. The investigator will (1) notify the participant's/partner's physician that the participant was being treated with AG-86893, and (2) follow the progress of the pregnancy to term and the health of the child to 12 months of age, by the participant or partner as appropriate, providing written informed consent for release of this data. The investigator should document the outcome of the pregnancy and provide a copy of the documentation to Allgenesis.

## 9 STATISTICAL CONSIDERATIONS

### 9.1 STATISTICAL HYPOTHESES

The null hypothesis is that there is no difference between AG-86893 and AG-86893 vehicle in the change from baseline to Day 28 in the overall conjunctival hyperemia score. The alternative hypothesis is that the active group is different from vehicle in the change from baseline to Day 28 in the overall conjunctival hyperemia score.

### 9.2 SAMPLE SIZE DETERMINATION

As this is an exploratory study, an empirical sample size has been used.

Per sample size calculation using SAS Proc Power procedure, assuming the standard deviation of the mean overall hyperemia score is around 1.0, a study with 20 participants in each group (N=60)

should have at least 90% statistical power to detect a minimal difference of 1 in mean overall hyperemia scores among the three study groups at 95% confidence level.

For each of the 3 AG-86893 dose groups (vehicle, 0.1%, and 0.3%), approximately 20 participants with pterygium exhibiting conjunctival hyperemia are planned to complete the study. Therefore, a total of approximately 70 participants will be enrolled at up to 12 sites in order to achieve an estimated 60 evaluable participants after accounting for potential drop-outs. No more than a total of 70 participants will be enrolled in the study unless requested by Allgenensis.

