## 1 PROTOCOL SUMMARY

### 1.1 SYNOPSIS

Title:	A Multicenter, Prospective, Randomized, Double-Masked, Phase 2 Study Evaluating the Safety, Tolerability, and Efficacy of Topical AG-86893 in Patients with Pterygium
Short Name:	SURPH: a S t U dy of the R esponse to AG-86893 in patients with P terygium H yperemia
Study Description:	
Study Hypotheses:
 

• AG-86893 has an acceptable safety profile as measured by the incidence and severity of adverse events (AEs) compared with vehicle

• At least 1 concentration of AG-86893 is effective, as measured by the mean change from baseline in conjunctival hyperemia, compared with vehicle

 
Study Design:
 

• This is a multicenter, randomized (1:1:1), double-masked, vehicle-controlled, parallel-group, dose-response (0.1% and 0.3% AG-86893) study

• Participants will administer a single eye drop of study drug 3 times daily (TID) for 28 days to the study eye

• The duration of the study is 12 weeks, with 4 weeks of treatment with study drug and 8 weeks of follow-up without medication

Objectives:	
Safety Objective:
 

• Evaluate the safety and tolerability of AG-86893 eye drops in participants with pterygium

 
Efficacy Objectives:
 

• Evaluate the dose response of AG-86893 on conjunctival hyperemia

• Evaluate the dose response of AG-86893 on pterygium vascularity, volume and vessel length (exploratory)

 
Pharmacokinetic Objective:
 

• Determine plasma concentrations of AG-86893

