## 4 STUDY DESIGN

### 4.1 OVERALL DESIGN

The clinical hypotheses for this study are:

- AG-86893 has an acceptable safety profile, as measured by the incidence and severity of AEs compared with vehicle
- At least 1 concentration of AG-86893 is effective, as measured by the mean change from baseline in overall conjunctival hyperemia compared with vehicle

This will be a Phase 2, multicenter, prospective, randomized, parallel-group, double-masked study evaluating the safety, tolerability, and efficacy of AG-86893 topical eye drops in participants with pterygium who are at least 18 years of age with overall conjunctival hyperemia score  $\geq 2$  in the study eye. A central reading center will assess conjunctival hyperemia from ocular photography at the screening visit to qualify participant eligibility; in addition, the reading center will assess subsequent visits for conjunctival hyperemia, pterygium vascularity, pterygium volume and vessel length in a masked fashion, to determine efficacy.

The study will have 3 treatment groups—vehicle, 0.1% AG-86893, and 0.3% AG-86893—with participants being randomly assigned in a 1:1:1 ratio to study drug. Study drug will be administered only to the selected study eye, until the Day 28 visit. Compliance with the study drug regimen will be estimated by weighing both eye drop bottles at Day 7 (if visit conducted in-clinic) and again at Day 28.

There will be 6 possible clinic visits, including a 14-day screening period (from Day -14 to -2), followed by a treatment/observation period (Day 1, Day 7 [may be conducted as a phone follow-up], and Day 28), and 2 post-treatment follow-up visits for safety monitoring (Day 56 and Day 84).

Collection of anterior-segment optical coherence tomography (AS-OCT) imaging will be done at sites with the requisite equipment and certified by the reading center. Plasma drug monitoring will be done at selected sites with the required facilities.

Primary database lock will occur after all participants exit the study on Day 84. Assessment of safety, tolerability, efficacy, and plasma concentrations of AG-86893 requires participants to participate for 12 weeks from Baseline to Study Exit (Day 84), plus the 2- to 14-day screening period.

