#### 4.3 JUSTIFICATION FOR DOSE

The doses selected in this study were based on the doses that were found to be effective in inhibiting new blood vessel growth on the cornea in a rabbit model. In that study, doses of 0.1%, 0.3%, and 1% were equally effective in inhibiting the blood vessel growth caused by suture placement. Rabbits dosed QID bilaterally for 7 days at doses of 0.3%, 0.6%, and 1% showed no signs of discomfort or ocular irritation. These doses were tested for safety and ocular histopathology in a 28-day GLP rabbit and monkey study after topical TID dosing of AG-86893. All the doses tested were safe and 1% identified as the NOAEL (no-observed-adverse-effect-level) dose. It is therefore expected that the doses of 0.1% and 0.3% administered TID will be tolerable and safe, and that at least 1 concentration will be effective in reducing hyperemia in participants with pterygium.

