### 9.3 POPULATIONS FOR ANALYSES

Three analysis populations will be defined and used in the statistical analyses: (1) a safety population, (2) a modified intent-to-treat (mITT) population, and (3) a per-protocol (PP) population.

Safety analyses will evaluate all randomized participants who received at least 1 dose of study drug and attended a post-baseline visit. Results will be presented based on the treatment received.

The primary statistical analyses will evaluate the mITT population, defined as all randomized participants who received at least 1 dose of study drug and had conjunctival hyperemia evaluated at both the Day 1 and Day 28 visits. Results will be presented based on the treatment assigned during randomization.

As a sensitivity analysis, the primary efficacy endpoint of conjunctival hyperemia will also be evaluated in the PP population of participants, who had no major protocol violations. Nominal data will be analyzed using the Pearson chi-square test or Fisher exact test. Conjunctival hyperemia, pterygium vascularity, BCVA, ophthalmoscopy, AS-OCT, and IOP data will be analyzed using analysis of variance models with dose strength as main effects. The analysis will be based on observed data. Missing values will not be imputed.

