3.3 Sample Size Considerations

An empirical sample size estimation was used as this is an exploratory study. Approximately 20 evaluable study participants are planned for each treatment group. Therefore, a total of approximately 70 participants will be enrolled at up to 12 sites in order to achieve a planned 60 evaluable participants after accounting for potential drop-outs.

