6.5 Efficacy Evaluation

All efficacy analyses will be based on the mITT population.

The primary statistical approach for assessment of difference among the treatment groups in change from baseline to Day 28 in conjunctival hyperemia score will be based on a mixed effect model. Significant baseline characteristics and their interaction might be included as covariant. Mean changes for each treatment group and the differences in mean changes will be estimated with the Least-Square means generated by the mixed model. Multiplicity adjustment will be conducted with Bonferroni approach.

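### The protocol's power of at least 90% is the best case of the overall F-test (79% with evenly spaced means); under the SAP's pairwise rule a named dose has about 75%

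*Protocol*

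**What the plan says.** Protocol 9.2 calls the sample size empirical and then gives a power statement from SAS Proc Power. "assuming the standard deviation of the mean overall hyperemia score is around 1.0", a study with 20 per group (60 in total) "should have at least 90% statistical power to detect a minimal difference of 1 in mean overall hyperemia scores among the three study groups", at the 95% confidence level. It gives neither the Proc Power test nor the pattern of the three means.

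Protocol 9.3 says that conjunctival hyperemia "will be analyzed using analysis of variance models with dose strength as main effects". The efficacy hypothesis in protocol 4.1 is: "At least 1 concentration of AG-86893 is effective, as measured by the mean change from baseline in overall conjunctival hyperemia compared with vehicle". The synopsis objective is: "Evaluate the dose response of AG-86893 on conjunctival hyperemia".

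SAP 6.5.1 tests the primary endpoint in two steps. A global treatment test at alpha 0.05 comes first. If it is significant, three Bonferroni-adjusted pairwise comparisons follow: each dose against vehicle, and dose against dose. The code in SAP Appendix 2 matches. SAP 3.3 repeats the sample size ("An empirical sample size estimation was used as this is an exploratory study") and gives no power figure.

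**The concern.** There are two problems.

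- **The pattern of means is missing.** The power of a three-group F-test depends on where the middle mean lies, not only on the largest difference. A power given as a minimum should hold wherever the middle mean lies, or the pattern should be stated.
- **The figure covers only the first step.** A significant global test does not show which groups differ. The hypothesis that a concentration beats vehicle is settled at the pairwise step, at alpha 0.05/3, and neither document gives power for it.

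A reader who relies on the protocol would expect a true 1-point effect to be missed at most one time in ten. For a named dose under the SAP rule it is missed about one time in four. A non-significant dose could then be read as ineffective with more confidence than the design supports, and SAP 6.5.1 uses the pairwise step for dose selection.

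**Working it through.** **Inputs.** n = 20 per group, SD = 1.0, difference = 1, alpha = 0.05 (protocol 9.2); two-sided tests (protocol 9.4.1); one-way ANOVA on dose (protocol 9.3); global test, then Bonferroni over three pairs (SAP 6.5.1 and Appendix 2). No covariates. Means are listed as distances in points, vehicle first.

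**Step 1: reproduce the protocol's figure.** Overall F-test, noncentral F with 2 and 57 degrees of freedom, λ = n·Σ(μᵢ − μ̄)²/SD².

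For (0, 1, 1) the overall mean is 2/3, so Σ = 4/9 + 1/9 + 1/9 = 2/3 and λ = 20 × 2/3 = 13.33. Power = 89.97%, and (0, 0, 1) gives the same. This is the source of the 90%.

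**Step 2: move the middle mean, keeping the largest difference at 1.**

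| Means | λ | Power of overall F-test |
|---|---|---|
| (0, 0, 1) or (0, 1, 1) | 13.33 | 90.0% |
| (0, 0.1, 1) | 12.13 | 86.9% |
| (0, 0.25, 1) | 10.83 | 82.6% |
| (0, 0.5, 1) | 10.00 | 79.3% |

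Σ is greatest when the middle mean coincides with an end and least when it is central, so 90% is the maximum and 79.3% the minimum. With even spacing, 90% needs a range of 1.16 or an SD of 0.87.

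**Step 3: one dose against vehicle at the SAP's alpha.** Noncentral t, 57 degrees of freedom, alpha 0.05/3 = 0.0167, noncentrality = 1/(1.0 × √(2/20)) = 3.16, critical value 2.467. Power = 75.4%. A power of 90% needs a difference of 1.19 or an SD of 0.84.

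**Step 4: the full SAP rule.** Simulation with 1,000,000 trials per pattern, pooled variance: F-test at 0.05, then Bonferroni pairs.

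| Means (vehicle first) | Dose 1 point from vehicle | At least one dose | Both doses |
|---|---|---|---|
| (0, 0, 1) | 75% | 76.0% | – |
| (0, 0.25, 1) | 75% | 75.3% | – |
| (0, 0.5, 1) | 75% | 76.1% | – |
| (0, 0.75, 1) | 75% | 80.0% | – |
| (0, 1, 1) | 75% | 87.9% | 63.0% |

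The named-dose results lie between 75.1% and 75.4%. If vehicle lay midway between the doses, which is unlikely, at least one dose would have 38%.

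**Step 5: sensitivity to SD and covariates.** Named dose, as in step 3: 93% at SD 0.8, 85% at 0.9, 66% at 1.1 and 57% at 1.2.

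SAP 6.5 says "Significant baseline characteristics and their interaction might be included as covariant". The documents give no correlation, so the values below are assumptions. The residual SD is √(1 − r²), ignoring the lost degrees of freedom.

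| Assumed r | Residual SD | F-test, even spacing | Named dose | At least one dose, both at full effect |
|---|---|---|---|---|
| 0.3 | 0.954 | 83% | 80% | 91% |
| 0.5 | 0.866 | 90% | 88% | 95% |

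**The case against.** **The number is right for a plausible pattern.** It is correctly calculated for two equal means. Protocol 4.3 reports that in rabbits "doses of 0.1%, 0.3%, and 1% were equally effective in inhibiting the blood vessel growth caused by suture placement", which fits vehicle at 0 and both doses at 1. Even spacing is a scenario introduced here, relevant to the dose-response objective. This stands, but the pattern is still unstated. Even under it, the SAP rule gives 88% for at least one dose and 75% for a named dose.

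**The 1-point difference may be a smallest difference.** If every pair differed by at least 1, as in (0, 1, 2), F-test power would be 99.99% and the sentence literally true. That calculation does not produce 90%, so it is not the source of the figure.

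**The sentence describes the overall test, and the Bonferroni alpha appears only in the SAP.** This is true, and the 75% does depend on the SAP's alpha. But an unadjusted two-sided pairwise test at 0.05 with 57 degrees of freedom still reaches only 87.5%.

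**The analysed number may exceed 20 per group.** The mITT set needs grading only to Day 28, and 70 are to be enrolled. With 23 per group, close to the upper limit (70/3 = 23.3), the F-test has 93.9% (two equal means) or 85.2% (even spacing). A named dose has 82%, and at least one dose has 92% if both have the full effect. This is a fair qualification, but the protocol attaches its claim to 20 per group, and the named-dose figure stays below 90%.

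**The study is exploratory and the SD approximate.** Both are true, and they limit the consequence. They do not make the printed minimum correct.

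**Conclusion.** The concern holds. The protocol's figure is correctly calculated but wrongly described. It is the maximum of the overall F-test for a largest difference of 1, and that power falls to 79% with evenly spaced means. It does not carry over to the dose-against-vehicle step, where a named dose has about 75%, at least one dose 75% to 88%, and both doses together 63%.

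These figures assume 20 analysed per group, an SD of 1.0, no covariates and, for the pairwise step, vehicle at one extreme. A smaller SD, useful covariates or more analysed participants would raise them; a larger SD would lower them. The protocol attaches its SD to the hyperemia score, whereas the endpoint is change from baseline, so the SD meant should also be confirmed.

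The design is not invalidated. The power statement should be corrected.

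**What to change.** Replace the power sentence in protocol 9.2 with wording such as:

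> With 20 evaluable participants per group and an assumed SD of 1.0 for the change from baseline [or the SD actually meant], the overall ANOVA F-test at two-sided alpha 0.05 has 90% power if two group means are equal and the third differs by 1.0, and 79% if the means are evenly spaced over a range of 1.0. Under the SAP rule (global test, then Bonferroni over three pairs, no covariates), with vehicle at one extreme, power is about 75% for a named dose 1.0 from vehicle. For at least one dose it is about 75% if one dose has the full effect and the other at most half of it, and about 88% if both have the full effect. Power of 90% for a named dose corresponds to a difference of about 1.2.

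Add the named-dose sensitivity to the SD (about 93% at 0.8 and 57% at 1.2), and note that covariate adjustment could raise these figures. Carry the same statement into SAP 3.3.

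The cost is wording in two sections and a less favourable stated power. Enrolment, test, endpoint and alpha stay as they are.
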